APPENDIX 6. MULTIPLE IMPUTATION AND TIPPING POINT ANALYSIS

For the primary 4-component MACE endpoint (MACE-4), the multiple imputation and tipping point (TP) analyses are comprised of the following steps:

Step 1. Model for Unobserved Events

A parametric exponential survival model (e.g., PROC LIFEREG in SAS) is used for the events after stopping the assigned treatment. Specifically, when fitting the model, the start time of each patient is the date of the last dose. The event or censoring time remains the same as in the primary analysis. Patients who had events prior to the last dose will not be included in the analysis. Treatment assignment is included as a covariate and the parameters are intercept α , and β which is the log hazard ratio between active treatment and placebo groups after they have stopped the assigned treatment.

Step 2: Simulation of Unobserved Events

For patients who were censored (i.e., did not experience a MACE-4), a time to event is simulated from the fitted model in Step 1, and it is added to the date of last dose for each patient.

Afterwards, all patients are censored at the calendar date of [REDACTED] or their date of non-CV death.

[figure not shown]
- For multiple imputation, the parameters $(\tilde{\alpha}, \tilde{\beta})$ will be drawn from a bivariate normal distribution centered around the MLEs $(\hat{\alpha}, \hat{\beta})$ with the model-based variance-covariance matrix. This is an approximate to the posterior distribution of the parameters when a flat non-informative prior is used.
- For TP, $\hat{\alpha}$ is used. However, instead of the observed treatment effect $\hat{\beta}$, a range of values (from hazard ratios of 1.00 to 1.10 in 0.01 increment) will be used to allow the patients assigned to the active treatment to have the same or event worse outcome than those assigned to the placebo group after dropping out and stopping the treatment.

[figure not shown]
A total of 100 datasets will be simulated for each scenario.

[figure not shown]
Step 3: Fitting Cox PH Model using Simulated Data and Final Inference

[figure not shown]
For each simulated dataset, a Cox PH model is used to estimate the difference (log hazard ratio) between the active treatment and placebo groups.

[figure not shown]
The resulted estimates are combined using Rubin's method (Rubin, 1987), e.g., using PROC MIANALYZE in SAS.

[figure not shown]

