7. STUDY DEFINITIONS

7.1. Disposition

Study Completion: the study completion status is recorded on the *Study Completion/Early Termination* CRF. A patient is considered as having completed the study if the patient completed the designated EOS visit during the study closeout period (as determined by the site), or if the patient died during the study (i.e., had not been discontinued prior to death).

Treatment Completion: the treatment completion status is recorded on the *End of Treatment* CRF. A patient is considered as having completed study treatment if the patient is still on-

treatment (i.e., has not permanently discontinued treatment) at the EOS visit during the study closeout period or died within 30 days of last dose. Note that patients who did not complete the study will not be considered as having completed the study treatment.

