8. STATISTICAL CONSIDERATIONS

8.1. Sample Size

This event-driven study is designed to provide at least 90% power to detect an approximate 15% relative risk reduction in hazard ratio corresponding to the primary composite MACE endpoint (CV death, nonfatal MI, nonfatal stroke, or coronary revascularization) at an overall study significance level (alpha) of 0.05. There are no interim efficacy analyses.

A statistical relationship between on-treatment LDL-C differences between the bempedoic acid group and the placebo group and CV event risk reduction is used to derive the postulated treatment effect of 15% stated above. Assuming a 3.59% annual event rate in the placebo group, a minimum of 1620 primary composite MACE events are needed.

The average follow up duration for all patients is estimated to be approximately 42 months (~3.5 years), with an enrollment phase of approximately 33 months, a minimum follow up duration of 24 months (2 years), and a lost-to-follow-up (LTFU) rate of 1% per year. Based on these assumptions, approximately 14,000 patients (approximately 7000 in the bempedoic acid group and 7000 in the placebo group) were randomized into the study to achieve 1620 patients experiencing an adjudicated primary endpoint event.

It is expected that at least 50% of the 1620 patients experiencing an adjudicated primary 4 component MACE (810 patients) will experience an adjudicated 3 component MACE (CV death, nonfatal MI, or nonfatal stroke). Therefore, the study will not stop until at least 1620 patients have experienced an adjudicated primary MACE endpoint, with 810 patients experiencing an adjudicated 3 component MACE, and a minimum of 24 months (2 years) have elapsed since the last patient was randomized.

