8.3. Multiplicity

There are one primary and six key secondary efficacy endpoints of interest for statistical testing in this study. A gatekeeping or hierarchical approach is used to test the primary efficacy endpoint and then key secondary efficacy endpoints sequentially to preserve the study-wise Type I error rate at 5%. For each endpoint, the null hypothesis is that of no difference between bempedoic acid and placebo groups, and the order for the hierarchical testing is:

1. time to first occurrence of MACE (CV death, nonfatal MI, nonfatal stroke, or coronary revascularization; primary 4-component MACE)
2. time to first occurrence of the composite endpoint of CV death, nonfatal MI, or nonfatal stroke (3 component MACE)
3. time to first occurrence of fatal or nonfatal MI
4. time to first occurrence of coronary revascularization

5. time to first occurrence of fatal or nonfatal stroke
6. time to CV death
7. time to all-cause mortality

For the final analysis of the differences between bempedoic acid and placebo, each hypothesis in this hierarchical order will be tested at a two-sided significance level of 0.05. Statistical significance at each step is required in order to test the next hypothesis. If any of the endpoints does not reach statistical significance, p-values for subsequent endpoints will be reported for information only.

For other efficacy and safety endpoints, a nominal p-value may be reported for information only.

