15.2.4. Sensitivity Analyses of Primary Efficacy Endpoint

In the primary analysis, censoring is assumed to be uninformative, i.e., patients who were censored share a common hazard function as those who were not censored in the same treatment group. However, there is a key difference between them as the censored patients also by definition stopped the treatment, while the majority of those remained on-study were still on-treatment. To evaluate the potential impact, two sensitivity analyses will be performed:

- Multiple imputation analysis: the hazard function for patients after censoring is assumed to be the same as those patients who were assigned the same treatment, had stopped treatment but remained in the study follow-up longer. The data from those patients with follow-up will be used as the model for imputation of the time to events for the censored patients.
- Tipping point (TP) analyses: The goal of this analysis is to explore the plausibility of unobserved data assumptions under which the conclusions change. Unlike the standard multiple imputation analysis, the censored patients in the active treatment group are allowed to have the same or even worse outcome than those in the placebo group. A range of assumed hazard ratios (vs placebo) will be used to evaluate when the estimated treatment effect starts to “tip”, i.e., becoming in favor of the placebo.

The details of the analyses are specified in Appendix 6.

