15.4.2. On-Treatment Analysis

An on-treatment analysis will also be conducted for primary time to 4-component MACE (MACE-4) and 3-component MACE (MACE-3) endpoints in the PPS.

The sensitivity analyses will also be performed for the time to first occurrence of NODM on treatment for patients with baseline glycemic status of no diabetes, prediabetes, or normoglycemic in the PPS.

For these on-treatment analysis, events (MACE-4, MACE-3 or NODM) that occurred after DLDOSE + 30 days will be ignored. Patients who did not have events before that will be censored at the earlier of the DLDOSE + 30 days and DLASMT, the date of censoring for non-fatal events defined in Section 7.2.5.

[figure not shown]
On-treatment analyses will be performed for lipid parameters and biomarkers including LDL-C, HDL-C, non-HDL-C, total cholesterol, triglyceride, hs-CRP, HbA_{1C} and fasting glucose. For these endpoints, values measured more than 7 days after the Date of Last Dose of IMP will be excluded, and only observed values prior to that will be summarized by treatment groups, and for HbA_{1C} and fasting glucose also by baseline glycemic status.

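### SAP Appendix 6 Step 1 leaves no gap after the last dose, so CV deaths on drug are fitted as post-discontinuation events and the imputation hazard is biased upward by an amount the documents do not fix

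*SAP*

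**What the plan says.** SAP Section 15.2.4 plans a multiple imputation and a tipping-point analysis to test whether censoring in the primary analysis was uninformative. It describes the donors for the imputation as patients on the same assigned treatment who "had stopped treatment but remained in the study follow-up longer".

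Appendix 6 puts this into practice.

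- **Step 1** fits an exponential model, with treatment as covariate, to events after the assigned treatment has stopped. In that fit "the start time of each patient is the date of the last dose". Event and censoring times stay as in the primary analysis. The only exclusion is: "Patients who had events prior to the last dose will not be included in the analysis".
- **Step 2** draws a time to event for each censored patient and adds it to the date of last dose. The multiple imputation draws both the intercept (alpha) and the log hazard ratio (beta). The tipping-point analysis keeps the fitted alpha but replaces beta with fixed hazard ratios from 1.00 to 1.10.

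Elsewhere the SAP treats the days just after the last dose as on-treatment. In Section 15.4.2, "events (MACE-4, MACE-3 or NODM) that occurred after DLDOSE + 30 days will be ignored". In Section 7.1, a patient who "died within 30 days of last dose" can count as having completed treatment.

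**The concern.** A patient who dies of a CV cause while taking study drug has a last dose on or just before the day of death. That death is never before the last dose, so Step 1 keeps it, with a time of roughly 0 to 1 day. A nonfatal MI, stroke or revascularization that ends dosing is also kept if it is dated on or after the last dose. A nonfatal event after which dosing continued is removed.

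The fit therefore gains events with almost no person-time, from patients who had no off-drug follow-up in the sense of Section 15.2.4. The same death is on-treatment in Section 15.4.2 and post-discontinuation in Appendix 6.

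At stake is whether the two analyses use the off-drug hazard they say they use. Alpha feeds both. Beta feeds only the multiple imputation, where it could carry part of the on-drug effect into patients who have stopped.

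**Working it through.** **Design figure first.** The documents give no figure for the Appendix 6 hazard. The design inputs used below do reproduce. Section 8.1 asks for "at least 90% power to detect an approximate 15% relative risk reduction in hazard ratio" "at an overall study significance level (alpha) of 0.05", and Section 8.3 makes it two-sided: "each hypothesis in this hierarchical order will be tested at a two-sided significance level of 0.05".

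- Schoenfeld events = 4(1.960 + 1.282)² / (ln 0.85)² ≈ 1592; Freedman gives 1599. Both are within 3% of 1620.
- Power with 1620 events is 90.5% at HR 0.85 and 96.3% at HR 0.83.

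**Inputs from the documents (SAP 8.1, 4.1):** placebo rate 3.59%/yr, 33-month accrual, loss to follow-up 1%/yr, 1:1 allocation of about 14,000, a stop at 1620 events and at least 24 months after the last entry.

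**Assumptions, not in the documents:**

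- stopping rate 3–15%/yr
- CV death as 10–30% of first MACE
- 0–10% of on-drug nonfatal MACE ending dosing
- on-drug deaths dated 1 day after the last dose
- on-drug HR 0.85 for every component
- true off-drug hazard 3.59%/yr in both arms (HR 1.00)

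**Formula.** The exponential rate is events divided by person-years from the last dose. The misplaced events add almost nothing to the denominator, so

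inflation ≈ 1 + (on-drug events kept) / (genuine off-drug events).

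**Central case** (6%/yr stopping, 20% CV death, no MACE ending dosing). Of the 1620 first events, 1620 × 0.20 = 324 are CV deaths. About 290 fall on drug and enter Step 1.

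- As written: 510 / 6,100 person-years = 8.4%/yr.
- Without the on-drug deaths: (510 − 290) / 6,100 = 3.6%/yr.
- Ratio 1 + 290/220 = 2.3.

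**Other cases, no MACE ending dosing:**

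| Stopping/yr | CV-death share | On-drug deaths / all fitted events | Person-years | As written | Ratio to 30-day lag |
|---|---|---|---|---|---|
| 10% | 10% | 135 / 456 | 9,050 | 5.0%/yr | 1.41 |
| 10% | 20% | 271 / 586 | 9,008 | 6.5%/yr | 1.87 |
| 15% | 10% | 120 / 546 | 12,160 | 4.5%/yr | 1.27 |
| 15% | 30% | 358 / 795 | 12,201 | 6.5%/yr | 1.81 |

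Over all 24 combinations the fitted hazard is 4.5–19.0%/yr, a ratio of 1.27–5.25. A second grid (CV-death share 5–20%, stopping 5–12%/yr, 0–10% triggered stops) gives 1.2–3.5. A 30-day lag returns 3.5–3.7%/yr throughout, which recovers the assumed 3.59%.

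**Sensitivity to the one-day gap.** If half of the on-drug deaths fall on the last-dose date and are lost as zero times, the ratio over the first grid (CV deaths only) is 1.14–2.77. With 10% CV death and 8%/yr stopping, the hazard is 5.7%/yr with a one-day gap (placebo arm), 4.6%/yr with half at zero, and 3.5%/yr with all at zero. In the last case there is no inflation.

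**Beta.** With a true off-drug HR of 1.00, the fitted HR is 0.86–0.96 on the first grid and 0.89–0.97 on the second. If CV death has no on-drug benefit, it is about 0.98.

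**Final hazard ratios.** The cutoff date in Step 2 is blacked out in the public copy, so closeout is assumed.

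| Scenario | MI: as written / 30-day lag | Tipping point at HR 1.00: as written / 30-day lag |
|---|---|---|
| 10% CV death, 8%/yr stopping | 0.882 / 0.888 | 0.892 / 0.893 |
| Same, 10% triggered stops | 0.880 / 0.883 | 0.904 / 0.885 |
| 20% CV death, 5%/yr, 10% triggered | 0.859 / 0.868 | not run |
| Central case | not run | 0.890 / 0.876 |

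**Step 2.** In the central case at HR 1.00, adding the draw to the last dose gives about 450 imputed events with the Step 1 hazard as written and about 197 with the landmark hazard (3.59%/yr). Drawing from the censoring date instead gives about 74 and 33. The difference arises because Step 2 can place an event inside follow-up already observed to be event-free.

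**The case against.** A reader might infer that the hazard is certain to be far too high, that neither sensitivity analysis is usable, or that the drug is materially favoured. The documents do not support any of these.

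- **Size.** They give no CV-death share, stopping rate or rate of MACE-triggered stopping. Dosing is daily, so death on the last-dose date is plausible, and Section 7.2.1 caps an imputed last dose at the end-of-study date, which can also make the dates equal. A zero time cannot contribute to the exponential fit in the example procedure unless a day is added, and the SAP does not say whether one is. This stands, and it is why the range reaches down to no inflation.
- **Nonfatal events.** Protocol Section 10.6 expects dosing to continue after an endpoint unless that is no longer clinically appropriate, and patients dosed past the event are excluded. This stands. The CV-death route is enough alone: the central case uses no triggered stops.
- **Tipping point.** Only alpha carries over. Extra events at hazard ratios of 1.00 or more pull the result toward no effect, and the analysis still varies the hazard ratio as Section 15.2.4 describes. This stands.
- **Beta.** The pull assumes that the drug reduces CV death itself; the SAP postulates 15% for the composite only. This stands, and the final shift was small even with that assumption.

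What does not fall is the conflict in the text. No section of the SAP removes on-drug deaths from Step 1.

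**Conclusion.** Step 1 is wrong as written: it does not deliver the donor group of Section 15.2.4, and it contradicts the on-treatment window of Section 15.4.2. The bias in alpha can only be upward. Its size, about 1.1 to 3.5 times or more, rests on assumed rates and an assumed true off-drug hazard of 3.59%/yr. It would be smaller if off-drug risk is really higher, and absent if all such deaths drop out as zero times.

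The practical reach is limited. The multiple-imputation hazard ratio shifted by 0.003 to 0.009 in favour of the drug in the scenarios checked, and the tipping-point error is conservative. The primary analysis uses no imputation (SAP 8.5), so its test and type I error are unaffected. The change should still be made, because it is cheap and these are the two analyses meant to answer the informative-censoring question.

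**What to change.** - **Step 1:** start each clock at the date of last dose plus 30 days, and fit only patients who are event-free and still in follow-up on that date. This uses the SAP's own window and yields donors as Section 15.2.4 describes them.
- **Step 2:** add the simulated time to each patient's censoring date, or to last dose plus 30 days if that is later, instead of to the last dose. Because the exponential model has no memory, this is the draw conditional on the event-free time already observed. Changing Step 1 alone would leave this second problem in place.

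The cost is a few sentences in Appendix 6 and a data filter, made before database lock and unblinding, when Section 5.3 says the SAP is finalized. Genuine off-drug events in the first 30 days leave the model, so the estimate is slightly less precise. Patients censored within 30 days of the last dose have no event simulated in the short remaining gap.

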7.2. Key Study Dates

7.2.1. Definition and Imputation of Key Event Dates

Date of End of Study (EOS): the study completion/early termination date recorded on the “Study Completion/Early Termination” CRF. Note that the patient may have a 30-day post EOS follow-up visit after this.

Date of Study Completion (DSC): For patients who did not complete the study, it is the later of a) the date of EOS and b) the date of the 30-day post EOS follow-up visit. For patients who completed the study, it is the latest date of a) the date of EOS, b) the date of the 30-day post EOS follow-up visit, or c) the date of death. This date is used to calculate the duration of study (follow-up) for each patient and all clinical events that happen during this period are adjudicated.

Date of First Dose of IMP (DFDOSE): for each patient, the DFDOSE is the date/time of administration recorded on the “On-Site Study Medication/ Compliance” CRF at Visit T1. If that field is missing, it is set to be next first date of administration at Visit T3.

Date of Last Dose of IMP (DLDOSE): the date of last dose is recorded on the End of Treatment CRF. In cases of missing either completely or partially, it is imputed as the earliest date of a) the last day of the month (if the month and year are present), or the last day of the year (if only the year is present); b) the Date of EOS; and c) the date of the last IMP dispense plus the number of tablets taken.

Date of Last Visit (DLVISIT): the last date recorded on either the *Visit Date* or the *Telephone Contact* CRFs. For patients who did not complete the study, this must be on or prior to the DSC.

Date of Last Known Alive (DALIVE): for patients whose vital status at the end of study is either alive or unknown, this is the last day when the patient is known to be alive. It is the latest “last known alive date” recorded on the *Survival Status* CRF. If this date is partially or completely missing, it is set to the later of last known alive date with imputation and DSC.

Date of Last Assessment for Non-Fatal Clinical Endpoints (DLASMT): Potential clinical endpoints are assessed every three months either in clinic or by telephone through the Post-EOS Phone visit. For patients who died during the study within 90 days of last visit, the DLASMT is set to the date of death. Otherwise, the DLASMT is set to be DLVISIT. Note that this definition also applies to new-onset diabetes mellitus (NODM) as an efficacy endpoint.

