15.2.3. Primary Efficacy Endpoint Data Censoring Pattern

For patients who were censored, i.e., did not experience MACE-4 endpoint, the pattern of censoring will be summarized by treatment, including

- censored for non-CV death
- censored on or after completion of the EOS visit during closeout
- censored prior to the study closeout period and not by non-CV death
- censored within 30 days of the last dose
- censored more than 30 days after the last dose

The total patient-year lost-to-follow-up will be calculated by treatment group as the sum of time from the date of censoring prior to study closeout and not by non-CV death, to the May 15, 2022 when the study closeout was initiated.

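### SAP Appendix 6 counts simulated events from last dose without requiring them to fall after censoring, so imputed MACE can land in follow-up already observed to be event-free

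*SAP*

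**What the plan says.** SAP 15.2.4 names two sensitivity analyses for the primary endpoint and sends the reader to Appendix 6 for details. Its stated assumption for the multiple imputation is that "the hazard function for patients after censoring is assumed to be the same as those patients who were assigned the same treatment", restricted to patients who had stopped treatment but were followed longer.

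Appendix 6 implements this as follows.

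- Step 1 fits an exponential model with time measured from last dose. Event and censoring times are kept as in the primary analysis, and patients whose event came before last dose are left out.
- Step 2 is headed "Simulation of Unobserved Events". It reads: "For patients who were censored (i.e., did not experience a MACE-4), a time to event is simulated". That time "is simulated from the fitted model in Step 1, and it is added to the date of last dose for each patient".
- The only later rule is an upper bound: "Afterwards, all patients are censored at the calendar date of" a redacted day, or at non-CV death.

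Other sections establish what is observed after last dose. Protocol 10.7.3 keeps patients in the study after permanent discontinuation of study medication (IMP). SAP 7.2.1 states: "Potential clinical endpoints are assessed every three months either in clinic or by telephone through the Post-EOS Phone visit". SAP 7.2.5 censors composites such as MACE-4 at the date of last assessment (DLASMT), not at last dose. SAP 15.2.3 plans to tabulate patients "censored more than 30 days after the last dose", and its patient-years lost to follow-up are "calculated by treatment group as the sum of time from the date of censoring prior to study closeout".

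**The concern.** Last dose is a coherent time origin, because Step 1 is fitted from it. What is missing is a lower bound. A patient who stopped IMP two years before DLASMT and had no event has two years of known event-free follow-up. Step 1 counts those two years as observed when it estimates the hazard; Step 2 then simulates over the same two years as if they were missing.

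These two analyses are the SAP's check on informative censoring of the primary endpoint. If many of the imputed events overwrite known data, the result depends partly on how many patients stopped IMP, and not only on how unfavourable the missing data would have to be. A sound primary result could then look more fragile than it is.

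**Working it through.** **The plan's own figure.** Appendix 6 states no numerical result. The nearest figure that can be checked is the 1,620 events for 90% power at HR 0.85, two-sided alpha 0.05 (SAP 8.1). Schoenfeld: 4 × (1.960 + 1.282)² / (ln 0.85)² gives 1,592 events; Freedman gives 1,599. Power with 1,620 events is 0.905. The plan's figure is reproduced closely.

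**Chance that one draw lands in observed time.** With hazard λ and t years of event-free follow-up after last dose, P = 1 − exp(−λt). At λ = 0.0359 per year (placebo rate, SAP 8.1):

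| t | P |
|---|---|
| 30 days | 0.3% |
| 1 year | 3.5% |
| 2 years | 6.9% |
| 3 years | 10.2% |

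Patients who complete on IMP have only the short gap to the post-EOS call. The exposure lies mainly with early stoppers. For them, observed survival exp(−λt) is multiplied by simulated survival exp(−λt), so under multiple imputation the off-drug hazard is roughly doubled.

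**Main simulation.**

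- From the documents: 14,000 patients 1:1, placebo rate 3.59%/yr, on-drug HR 0.85, loss to follow-up 1%/yr, EOS spread uniformly over 24-57.5 months (limits from the schedule of events), completers followed 30 days past EOS.
- Assumed, because not given or redacted: IMP stopping 3, 5 or 8%/yr; off-drug HR 0.85 or 1.0; non-CV death 1%/yr; cut-off at EOS, EOS + 30 days, EOS + 3 months or EOS + 6 months.
- Method: 3 × 2 × 4 = 24 scenarios, 100 trials × 10 imputations each, the same random draws for the as-written and corrected rules, Cox model per dataset, Rubin pooling.

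About 1,160-2,930 event-free patients have more than 30 days of observed follow-up after stopping IMP early, carrying about 2,170-5,590 person-years.

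| Quantity | As written | Corrected |
|---|---|---|
| Simulated events in observed time, multiple imputation | 69-221 | 0 |
| Simulated events in observed time, tipping point 1.10 | 76-233 | 0 |
| Tipping-point HR at 1.10 | 0.864-0.928 | 0.852-0.907 |
| Trials with tipping-point estimate reaching 1 (at 1.10) | 0-5% | 0-3% |

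The within-scenario shift in HR is +0.010 to +0.031 for tipping point 1.10, +0.005 to +0.019 for tipping point 1.00, and −0.001 to +0.013 for multiple imputation. The last is near 0 when the off-drug HR is 0.85 and positive when it is 1.0.

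The share of imputed events that fall in observed time depends on the cut-off:

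| Cut-off | Share in observed time | Corrected total imputed |
|---|---|---|
| EOS or EOS + 30 days | 72-89% | 26-31 |
| EOS + 3 months | 51-69% | 95-109 |
| EOS + 6 months | 34-52% | 197-226 |

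**Worked case** (8%/yr, off-drug HR 0.85, tipping HR 1.10):

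- Cut-off at EOS. As written: HR 0.884, mean upper limit 0.980, 197 of 226 imputed events in observed time. Corrected: 0.857, 0.951, 0 of 29. The remainder as written, 226 − 197 = 29, equals the corrected total.
- Cut-off at EOS + 6 months. As written: 0.906, 1.002, 233 of 452. Corrected: 0.881, 0.976, 0 of 222.

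Hand check for multiple imputation at EOS: about 5,350 observed off-IMP person-years × 0.034 per year ≈ 180 events, against 174 simulated.

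**Second simulation, coded separately** (33-month uniform accrual, 24-month minimum follow-up, off-drug HR 1.0, 20 trials × 20 imputations). Multiple-imputation branch:

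| Stopping/yr | Person-years after last dose, event-free patients | × 0.0359 | Simulated in observed time | All imputed, as written | All imputed, corrected |
|---|---|---|---|---|---|
| 3% | 1,157.4 × 1.7702 = 2,049 | 74 | 70 | 96 | 27 |
| 8% | 2,882.05 × 1.8222 = 5,252 | 189 | 182 | 209 | 27 |
| 12% | 4,036.1 × 1.8682 = 7,540 | 271 | 256 | 283 | 27 |

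The product λ × person-years slightly overstates the count because 1 − exp(−λt) is less than λt. Tipping-point HR at 1.10, as written against corrected: 0.864 and 0.854; 0.918 and 0.898; 0.903 and 0.871. Compare within rows only, because each row uses different random trials.

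**The case against.** The strongest reply is that Appendix 6 is silent on conditioning and does not rule it out. A conditional draw is also a time added to last dose, and 15.2.4 makes the intent clear, so a careful programmer might do it correctly. This does not rescue the text. 15.2.4 defers to Appendix 6 for the method, Step 2 includes everyone without a MACE-4, and its only bound is an upper one. Followed literally, it overwrites observed data. The redacted date cannot supply a lower bound.

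Other points stand in part.

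- Of the conflicting places, 15.2.4 carries the weight. The step heading and the descriptive patient-year count in 15.2.3 are supporting evidence only.
- The SAP's tipping criterion is that the estimate favours placebo, and that is rarely affected. The upper-limit result uses a criterion that the SAP does not set.
- The simulated trials have about 1,490-1,515 observed events, not the 1,620 at which the study stops, and use 10 imputations against the SAP's 100. Upper-limit crossing rates are probably somewhat overstated.
- Protocol 10.7.3 allows sparser telephone contact for some patients off IMP, so ascertainment in the interval may be less regular than quarterly. The primary analysis still treats the time to DLASMT as event-free, and the sensitivity analyses should start from the same data.
- The bias in the tipping-point analysis runs against the drug. That limits the harm, but an analysis meant to measure missing-data risk should not be driven by data that are not missing.

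**Conclusion.** The concern holds: Step 2 is wrong as written and does not implement the assumption in 15.2.4. Confidence in that textual defect is high. The size of the effect is conditional on the assumed stopping rate, off-drug HR, non-CV death rate and cut-off. Across the assumed ranges, simulated events in observed time make up from about a third to almost nine tenths of everything imputed. The effect on the pooled HR is modest and no conclusion from the primary Cox and log-rank analysis is at risk. The practical exposure is the confidence limit in the sensitivity analyses: in 3-26% of simulated trials it is at or above 1 as written but below 1 when corrected. This should be fixed, but it does not threaten the trial's main inference.

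**What to change.** In Step 2, measure the simulated time from each patient's censoring date (DLASMT). Equivalently under the exponential model, keep last dose as origin and draw conditional on the time exceeding the interval from last dose to DLASMT. State that only the period between censoring and the cut-off is imputed, and that patients observed to the cut-off receive no imputed event. Apply this to both the multiple-imputation and tipping-point branches, and align the wording with 15.2.4.

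Cost: one clause in Appendix 6 and one line of code. No new data are needed and the primary analysis does not change.
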